approximately 2 to 4 hours. The compound half-life ranges from 9 to 11 hours. Exposure (C_{\max} and AUC_{0-12}) to BVD-523, as well as selected metabolites, generally increased in a dose-related fashion from dose levels of 10 to 600 mg BVD-523 BID. At Day 1, a further increase in exposure was seen at 750 mg BVD-523 BID, but exposure was similar between 750 and 900 mg BID. At Day 15, no further increase in exposure was observed as the dose increased from 600 to 900 mg BVD-523 BID.

A single-dose, 2-way crossover study to evaluate the effects of food on the pharmacokinetics (PK), safety, and tolerability of an orally administered 600-mg dose of BVD-523 has been completed in healthy volunteers. Fourteen healthy volunteers were dosed in this study. Following single-dose oral administration of 600 mg BVD-523, the median T_{\max} occurred at 3.1 hours in fasted subjects and at 6.1 hours in fed subjects (high-fat breakfast). Overall, a total of 6 treatment-emergent AEs (TEAEs) were reported in 5 subjects (35.7%). There were no deaths or serious AEs (SAEs) reported during the study and no TEAEs that led to discontinuation of subjects. All TEAEs were transient and had resolved by the end of the study.

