4 INVESTIGATIONAL PLAN

4.1 Study Design

This study will be an open-label, absorption, metabolism, and excretion study of [¹⁴C]-BVD-523 administered as a 600-mg (approximately 200 µCi) oral dose to 6 healthy male subjects following a 2-hour fast from food (not including water) that follows breakfast.

A schematic of the study design is presented in [Figure 4-1](#). The start of the study is defined as the date the first subject signs an Informed Consent Form (ICF). This is specifically for a subject enrolled (assigned a dose) in the study and does not include screen failure subjects for clinical pharmacology studies. A subject who completes all PK, radioactivity, and metabolism sampling prior to Discharge is considered to have completed the study. This is the last planned contact with the subject, and does not include any unplanned follow-up (eg, return to the clinic for repeat clinical laboratory). The end of the study is defined as the date the last subject completes the study. The planned duration of study conduct is up to 43 days (Screening through Discharge).

Figure 4-1 Study Design Schematic

Screening	Check-in	Dosing	PK/Radioactivity Sampling	Study Completion ^a
Days -28 to -2	Day -1	Day 1	Day 1 to Study Completion	Day 8 to Day 15
← Confined to CRU →				

CRU = Clinical Research Unit; PK = pharmacokinetic.

^a Subjects will be discharged from the CRU starting on Day 8 if plasma radioactivity levels are below the limit of quantitation, ≥90% of the radioactive dose is recovered, and if ≤1% of the radioactive dose is recovered in urine and feces for 2 consecutive 24-hour collection intervals. If these criteria are not satisfied

by the morning of Day 8, subjects will continue to be confined in the CRU until these criteria are met, up to a maximum of Day 15.

Subjects will be confined at the clinical site from the time of Check-in until Discharge (between Days 8 and 15). After completing discharge procedures, subjects will be discharged from the clinical site on Day 15 or as early as Day 8, provided radioactivity has reached the following threshold values:

- Plasma radioactivity levels below the limit of quantitation; and
- $\geq 90\%$ of the dose is recovered; and
- Urine and fecal total radioactivity combined $\leq 1\%$ of the administered dose for 2 consecutive 24-hour intervals.

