Sample collection and confinement will continue until discharge criteria are met or the maximum stay is reached. Subjects experiencing emesis during the first 4 hours postdose may be discharged on the same day from the clinical site, provided there are no safety concerns, and after follow-up study procedures are performed.

In this study design, safety will be monitored with AE inquiries, clinical laboratory evaluations ([Appendix A](#)), vital signs measurements, 12-lead ECGs, and PE findings during the study.

Blood/plasma, urine, and fecal samples will be collected for bioanalytical, radioanalytical, and metabolism analysis through 168 hours postdose. If Discharge occurs after Day 8, additional samples (blood/plasma, urine, and fecal) for radioanalysis will be collected every 24 hours until Discharge. A study flow chart is presented in [Table 6-1](#).

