6 STUDY PROCEDURES

6.1 Schedule of Study Procedures

A study flow chart is presented in [Table 6-1](#). The total blood volume that will be taken during the study is outlined in [Appendix B](#).

Table 6-1 Study Flow Chart

Study Procedures	Screening (-28 to -2)	Check-in (Day -1)	Day 1	Day 2	Day 3	Day 4	Days 5 to 7	Discharge/Early Termination (Days 8 to 15)^a
Informed Consent	X							
Confined to the CRU		X	X	X	X	X	X	X
Demographics	X							
Medical History	X	X ^b						
Hepatitis and HIV Screen	X							
Drug Screen^c	X	X						
Height, Weight, and BMI	X	X ^d						
12-lead ECG^e	X	X						X
Vital Signs^f	X	X	X	X	X	X	X	X
Clinical Laboratory Evaluations^g	X	X						X
Physical Examination		X						X
Dose^h			X					
Blood Samples for PK/Radioactivity Analysisⁱ			X	X	X	X	X	X
Blood Samples for Metabolism Analysis^j			X	X	X	X	X	X
Urine Samples for PK, Radioactivity, and Metabolism Analysis^k		X	X	X	X	X	X	X
Fecal Samples for Total Radioactivity and Metabolism Analysis^l		X	X	X	X	X	X	X
SAE Monitoring^m	X	X	X	X	X	X	X	X
AE Inquiryⁿ		X	X	X	X	X	X	X
Previous Medication	X	X						
Concomitant Medication Monitoring		X	X	X	X	X	X	X

Abbreviations: AE = adverse event; BMI = body mass index; CRU = Clinical Research Unit;

ECG = electrocardiogram; HIV = human immunodeficiency virus; PK = pharmacokinetic; SAE = serious adverse event.

^a Early termination procedures are to be performed in close proximity to discontinuation of subject from the study.

Other procedures may be performed at Investigator (or designee) or Sponsor discretion.

^b Interim medical history only.

^c Drug screen does not include breath alcohol testing at Screening and does include breath alcohol testing at Check-in.

^d Height and BMI measured at Screening only.

^e Twelve-lead ECG will be collected after the subject has rested in the supine position for at least 5 minutes.

^f Vital sign measurements (oral body temperature, respiratory rate, and seated blood pressure and pulse) obtained at Screening, Check-in, 0 Hour (predose); 2, 4, and 24 (Day 2) hours postdose; and daily (24-hour intervals) up to and including day of discharge. Vital signs measurements should be carried out prior to having blood drawn, except at Screening and Day -1. Vital signs will be measured after the subject has been seated for at least 5 minutes.

^g Clinical chemistry panel (fasted at least 8 hours), complete blood count, and urinalysis.

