^h Single oral dose of [¹⁴C]-BVD-523 at 600 mg (approximately 200 µCi) administered orally after a 2-hour fast that follows breakfast.

ⁱ Blood samples for PK and radioanalysis collected at 0 Hour (predose); 30 minutes postdose; and 1, 2, 3, 4, 5, 6, 8, 12, 24, 48, 72, 96, 120, 144, and 168 hours postdose (Day 8). If subject is not discharged on Day 8, additional blood samples will be collected for radioanalysis every 24 hours until Discharge.

^j Blood samples for metabolite profiling and identification collected at 0 Hour (predose); 30 minutes postdose; and 1, 2, 3, 4, 5, 6, 8, 12, 24, 48, 72, 96, 120, 144, and 168 hours postdose (Day 8).

^k Urine samples collected at -12 to 0 (predose, the last void within 1 hour prior to dosing), 0 to 6, 6 to 12, and 12 to 24 hours postdose; and 24-hour intervals until Discharge.

^l Fecal samples collected predose (within 24 hours of dosing, if possible), from 0 to 24 hours postdose, and 24-hour intervals until Discharge.

^m Any SAEs occurring after the subject signs the Informed Consent Form will be collected.

ⁿ Subjects will be monitored for AEs beginning at initiation of study drug. An AE inquiry will be performed at Check-in and at each postdose vital sign measurement.

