6.2.3 Dose Preparation and Administration

Each unit dose will be prepared by qualified clinical staff. Each unit dose container will be appropriately labeled.

Appropriate unit doses, as described above, will be administered to consecutively-numbered subjects. Although the timing of events requires that each subject will be consistently administered the appropriate dose at specific times, the exact dose time of consecutive subjects may be staggered to obviate the need to have all subjects on precisely the same study schedule. For each dose, the subject's actual dose time will be recorded in the source documents and transcribed into the eCRFs.

Each dose will be administered orally with approximately 240 mL room temperature water. A hand and mouth check will be performed to verify that the dose administered was swallowed. After a 2-hour fast from food (not including water) that follows a standard high-fiber breakfast, doses will be administered. After a 1-hour fast from food (not including water) that follows dosing, a snack will be served. During the study, subjects may consume water ad libitum.

Except when they are using the toilet, study subjects will be observed for approximately 4 hours postdose. Note: Amount of time corresponds to the time postdose in which subjects with emesis could be replaced and is to ensure that they are not having AEs or becoming nauseated. Subjects will not lay supine for 1 hour following dose administration, except as necessitated by the occurrence of an AE(s) and/or study procedures.

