6.5.1 Adverse Events

Adverse event definitions; assignment of severity, causality, action taken, and outcome; and procedures for reporting SAEs are detailed in [Appendix C](#).

Subjects will be asked a nonleading question such as “Have there been any changes in your health status since Screening/since you were last asked?” at the timepoints specified in [Table 6-1](#) to assess for the occurrence of AEs. Subjects will also be encouraged to voluntarily report AEs occurring at any other time during the study.

All nonserious AEs, whether volunteered, elicited, or noted on PE, will be recorded from initiation of study drug until study completion. Nonserious AE information observed before dosing will not be listed as an AE in the eCRF but will be listed as medical history instead, unless the AE becomes more severe postdose, in which case it will be recorded as an AE in the eCRF. Serious AEs will be recorded from the time the subject signs the ICF until study completion.

All AEs (nonserious and serious) should be followed until the event has resolved, returned to baseline, or is assessed as stable by the Investigator (or designee).

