9. DEFINITION OF ANALYSIS POPULATIONS

The **All Subjects Population** will consist of all subjects who are enrolled in the study (signed the ICF) and have study assessments recorded in the electronic Case Report Form (eCRF).

The **Safety Population** will consist of all subjects who receive study drug and have at least 1 postdose safety assessment.

The **PK Population** will consist of all subjects who receive study drug and have evaluable PK data. Subjects may be excluded from the PK summary statistics and statistical analysis if a subject has an adverse event (AE) of vomiting that occurs within approximately 2 times median time to maximum concentration (T_{max}).

All protocol deviations that occur during the study will be considered prior to database lock for their severity/impact and will be taken into consideration when subjects are assigned to analysis populations. Details of subject assignment to the analysis populations will be listed.

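### Same-day discharge after early vomiting ends scheduled adverse-event inquiry on Day 1, with no later contact planned, for a subject who stays in the Safety Population

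*Protocol*

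**What the plan says.** Protocol Section 4.1 keeps subjects on site from Check-in until some day between Day 8 and Day 15. It makes one exception: subjects who vomit in the first 4 hours "may be discharged on the same day from the clinical site, provided there are no safety concerns, and after follow-up study procedures are performed". Discharge is optional. Section 6.2.3 observes all subjects for about 4 hours and describes this period as "the time postdose in which subjects with emesis could be replaced".

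The inquiry schedule is in Table 6-1 (Section 6.1). Footnote n says: "An AE inquiry will be performed at Check-in and at each postdose vital sign measurement". Footnote f sets the postdose vital signs at "2, 4, and 24 (Day 2) hours postdose; and daily (24-hour intervals) up to and including day of discharge". Neither the table nor the text schedules a telephone call or return visit after discharge. Of the end of sampling before Discharge, Section 4.1 says: "This is the last planned contact with the subject".

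Under Section 6.5.1, nonserious AEs "will be recorded from initiation of study drug until study completion". Serious AEs are recorded from consent to the same end point.

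The Safety Population in SAP Section 9 "will consist of all subjects who receive study drug and have at least 1 postdose safety assessment", and Protocol Section 7.2 agrees. The SAP's vomiting rule affects only the PK summaries.

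**The concern.** Safety and tolerability are the secondary objective, and the incidence, nature and severity of AEs are a stated endpoint. TEAEs are reported as numbers and percentages of subjects (SAP Section 10.4.1), with no allowance for length of observation. A man asked about AEs for less than a day therefore counts the same as one asked for 168 to 336 hours.

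After a Day 1 exit, a new event such as diarrhoea or rash would come to light only if the subject reported it unprompted. He has taken a 600-mg dose of which an unknown part was retained. There is also a subject-protection side: nobody is scheduled to ask a dosed healthy volunteer how he is on the following day.

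**Working it through.** The plan gives no figure of its own to reproduce here. The sample size rests on precedent (Protocol Section 7.1). The check is a count from the schedule, followed by a reading of the provisions that might fill the gap.

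**1. Scheduled postdose inquiries (Table 6-1, footnotes f and n)**

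| Stay | Scheduled times (h) | Total | From 24 h on (lost) |
|---|---|---|---|
| To Day 8 | 2, 4, 24, 48, 72, 96, 120, 144, 168 | 9 | 7 |
| To Day 15 | 2, 4, then every 24 h to 336 | 2 + 14 = 16 | 14 |

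The subject who leaves on Day 1 has the 2-hour and 4-hour inquiries, if still on site, plus one at exit. If the exit inquiry is counted as a third, the net shortfall is 9 − 3 = 6, or 16 − 3 = 13.

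**2. Timing against exposure (Protocol Section 2.1.2)**

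The half-life in patients is 9 to 11 hours. The first lost inquiry, at 24 hours, falls 24/11 = 2.2 to 24/9 = 2.7 half-lives after dosing. In the healthy-volunteer food study the median time to peak was 3.1 hours fasted and 6.1 hours fed. The 4-hour observation period can therefore end close to the peak, or before it, in a subject who kept the dose down.

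**3. Effect of one missed later event on the tables**

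- Any TEAE: change of 0, because vomiting after the dose already counts (SAP Section 10.4.1).
- Another preferred-term, organ-class, severity or relatedness count: one subject, so 1/6 = 16.7%, or 1/7 = 14.3% if a replacement is dosed.

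**4. Frequency**

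The documents give no rate of early vomiting in healthy subjects. As an assumption only, with per-subject probability p, the chance that at least one of six vomits early is 1 − (1 − p)^6. This gives 26.5% for p = 5%, 46.9% for p = 10% and 73.8% for p = 20%. These are chances of vomiting, not of early discharge or of a missed event.

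**5. Do other provisions fill the gap?**

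- The procedures required by Section 4.1 come before he leaves, and the early-termination assessments are done close to discontinuation. Both describe his state at exit.
- Sections 5.3 and 6.5.1 follow AEs already known until they resolve or stabilise. Vomiting that has settled by exit triggers no further contact.
- Section 6.5.1 encourages volunteered reports, but these are not a scheduled contact.

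**6. When does his AE recording end?**

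Section 6.5.1 ends recording at study completion. Section 4.1 defines a completer as someone who finishes all PK, radioactivity and metabolism sampling, which he does not do. Figure 4-1, however, uses the completion label for Days 8 to 15. On the first reading his window has no defined end. On the second it stays open, but nothing planned elicits events during it.

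**The case against.** The strongest case against is that the gap is narrow and already cushioned. A subject must vomit within 4 hours, raise no safety concern, be sent home by choice, and then have a new event that he does not report. Before leaving he has an ECG, vital signs, laboratory tests, a physical examination and an AE inquiry, and extra procedures are allowed at discretion. Vomiting may lower his exposure. The reports of common diarrhoea and rash come from patients on chronic dosing. Healthy volunteers given single 600-mg doses had 6 TEAEs in 5 of 14 subjects (35.7%), all transient and none serious. Stays beyond Day 8 are driven by radioactivity criteria, so the Day 15 comparison overstates what safety monitoring needs. Safety is summarised descriptively, and because AEs and disposition are listed, a reader can see the shortened observation.

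Most of this stands, and it limits the point to a minor one. The sentence on last planned contact is also written for completers, so the argument rests mainly on the absence of any later contact in the schedule. What the objection does not supply is a planned means of detecting new events after exit. The listings show that observation was short, but they cannot show an event that nobody asked about.

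**Conclusion.** The concern holds as a minor design point. Same-day discharge ends scheduled AE inquiry on Day 1, no later contact is planned, the subject stays in the safety denominator, and the end of his recording window is open to interpretation. The Day 8 comparison (7 of 9 inquiries lost, 6 net of the exit inquiry) is the fairer measure. The effect on any-TEAE incidence is nil, and the effect of one missed event on another row is one subject in six or seven. Neither the frequency nor the size of any under-count can be fixed from the documents. The half-life timing uses patient data and says nothing about AE risk after partial loss of the dose. Confidence is high that the scheduled contact is absent; no claim is made that the trial's safety conclusions would be biased.

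**What to change.** Keep same-day discharge and make two short protocol changes.

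- **Section 4.1 and Table 6-1, footnote n:** for subjects discharged on Day 1 after emesis, add an AE inquiry by telephone at nominal 24 hours and nominal Day 8.
- **Section 6.5.1:** state that AE recording for these subjects, serious events included, runs at least to the Day 8 call. Word this as a minimum so that it does not shorten any longer window.

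The SAP needs no change, since it already lists all AEs (Section 10.4.1) and disposition (Section 10.2). SAP Section 10.1 carries listings to the point of withdrawal, so the protocol wording should make the Day 8 call the end of participation for these subjects. Events found by telephone then appear in the listings.

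The cost is a few sentences and two calls for an occasional subject.

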4.2 Discussion of Study Design

This study is designed to characterize the absorption, metabolism, and excretion of BVD-523 using radiolabeled drug in healthy adult male subjects to support its further development and registration.

The study will be conducted as an open-label trial as the study measures are objective outcomes (eg, total radioactivity in select biological matrices, metabolite profiling/characterization). Conducting the study in healthy subjects will allow the evaluation of BVD-523 metabolism in the absence of concomitant medications. The dose, subject population, study duration, and sample collection timing are considered adequate to achieve the study objectives.

5 SUBJECT SELECTION

Subjects who meet all the inclusion criteria and for whom none of the exclusion criteria apply will be eligible to be enrolled into the study. Safety evaluations may be repeated at the Investigator's (or designee's) discretion.

Six subjects will be enrolled to have at least 4 subjects complete the study.

5.1 Inclusion Criteria

Subjects who meet the following criteria may be included in the study:

1. Males, between 18 and 65 years of age, inclusive, at Screening;
2. Have a body mass index range of 18.5 to 32.0 kg/m², inclusive, at Screening;
3. In good health, determined by no clinically significant findings from medical history, 12-lead ECG, and vital signs measurements at Screening or Check-in and PE findings at Check-in as determined by the Investigator (or designee);
4. Clinical laboratory evaluations (including clinical chemistry panel [fasted at least 8 hours], hematology/complete blood count [CBC], and urinalysis [UA]; [Appendix A](#)) within the reference range for the test laboratory at Screening and Check-in, unless deemed not clinically significant by the Investigator (or designee);
5. Negative test for selected drugs of abuse and cotinine at Screening (does not include alcohol) and at Check-in (does include alcohol; [Appendix A](#));
6. Negative hepatitis panel (including hepatitis B surface antigen and hepatitis C virus antibody) and negative human immunodeficiency virus (HIV) antibody screens ([Appendix A](#)) at Screening;
7. Males will be surgically sterile for at least 90 days (confirmed by documented azoospermia) or, when sexually active with female partners of childbearing potential, will agree to use contraception as detailed in [Section 6.3.3](#) from Check-in until 90 days following dosing;
8. Males must be willing to refrain from sperm donation from Check-in to 90 days from the day of dosing;
9. Able to comprehend and willing to sign an ICF;
10. A minimum of 1 bowel movement per day.

5.2 Exclusion Criteria

The following will exclude potential subjects from the study:

1. Significant history or clinical manifestation of any metabolic, allergic, infectious, dermatological, hepatic, renal, hematological, pulmonary, cardiovascular, gastrointestinal, neurological, or psychiatric disorder (as determined by the Investigator [or designee]) prior to Check-in;
2. History of significant hypersensitivity, intolerance, or allergy to any drug compound, food, or other substance, unless approved by the Investigator (or designee) prior to Check-in;
3. History of stomach or intestinal surgery or resection that could alter absorption or excretion of orally administered drugs prior to Check-in, except appendectomy and hernia repair will be allowed if it was not associated with complications;
4. History of Gilbert's Syndrome;
5. History or presence of an abnormal ECG that, in the Investigator's (or designee's) opinion, is clinically significant;
6. History of alcoholism or drug addiction within 1 year prior to Check-in;
7. History of nicotine use within 6 months prior to Check-in or positive cotinine at Screening or Check-in;
8. Participation in more than 1 other radiolabeled investigational study drug trial within 12 months prior to Check-in. The previous radiolabeled study drug must have been received more than 6 months prior to Check-in for this study and the total exposure from this study and the previous study will be within the recommended levels considered safe, per United States (US) Title 21 Code of Federal Regulations (CFR) 361.1 (eg, less than 3,000 mrem whole body annual exposure);
9. Exposure to significant radiation (eg, serial x-ray or computed tomography scans, barium meal, current employment in a job requiring radiation exposure monitoring) within 12 months prior to Check-in;
10. Use of any drugs or substances known to be strong inhibitors or strong inducers of CYP3A enzyme within 30 days prior to study drug administration, unless otherwise stated, and throughout the study;

11. Participation in any other investigational study drug trial in which receipt of an investigational study drug occurred within 5 half-lives (if known) or 30 days prior to Check-in, whichever is longer;
12. Use of any prescription medications/products within 14 days prior to Check-in, unless deemed acceptable by the Investigator (or designee);
13. Use of any over-the-counter, nonprescription preparations (including vitamins, minerals, and phytotherapeutic/herbal/plant-derived preparations) within 7 days prior to Check-in, unless deemed acceptable by the Investigator (or designee);
14. Poor peripheral venous access prior to Check-in;
15. Donation of whole blood from 56 days prior to Screening through Discharge, inclusive, or of plasma from 30 days prior to Screening through Discharge, inclusive;
16. Receipt of blood products within 2 months prior to Check-in;
17. Any acute or chronic condition that, in the opinion of the Investigator (or designee), would limit the subject's ability to complete or participate in this clinical study;
18. Any other unspecified reason that, in the opinion of the Investigator (or designee) or Sponsor, makes the subject unsuitable for enrollment.

